We hypothesize that preterm infants supplemented with early physiologic doses of L-carnitine while on parenteral nutrition will have improved short-term growth parameters and significantly higher neurobehavioral scores when compared with control infants.

Primary Aims:

To determine whether carnitine supplementation is associated with:

- 1. Decreased percent weight loss within the first two weeks of life and decreased length of time to regain birthweight.
- 2. Improved performance on the NICU Network Neurobehavioral Scale (NNNS) at 40 weeks postmenstrual age (+/- 2 weeks).

Secondary Aims:

To determine whether carnitine supplementation is associated with:

- 1. Increased rate of growth of head circumference within the first month of life and increased food efficiency (weight gain/calorie intake) during the supplementation period.
- 2. Normalization of the serum carnitine profile at two weeks of life, compared with infants born at a post-menstrual age 2 weeks later.
- 3. Enhanced brain maturation as measured by amplitude-integrated EEG (aEEG) measurements obtained during the hospital course
- 4. Fewer abnormal findings, better brain growth, white matter development and brain metabolism on brain magnetic resonance imaging (MRI) at 36-40 weeks' corrected age (prior to hospital discharge)

Because of the potential for systemic effects of L-carnitine supplementation, we will also monitor those variables which showed significant difference in our prior study: rates of proven infection, hearing screen failure and PDA ligation.

Primary Outcomes:

- 1. Length of time to regain birthweight,
- 2. Percent weight loss in the first two weeks of life,
- 3. Neurodevelopmental scores on the NICU Network Neurobehavioral Scale (NNNS) at 40 weeks post-menstrual age (+/- 2 weeks)

Methods/Design:

This is a prospective, randomized controlled clinical trial involving infants with gestational age (GA) <32 wks who are born at either the Jack D. Weiler Hospital or the Wakefield Division of Montefiore and admitted to theirNeonatal Intensive Care Unit. Informed consent will be obtained from the parents of eligible patients as early as possible within 72 hours of birth. Infants whose parents have signed an informed consent form will be randomized to receive either carnitine supplementation (50 µmol/kg/day) versus placebo within 72-96 hours of birth.

Inclusion criteria:

- Infants born <32weeks' gestation
- Exclusion criteria:
 - Presence of

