Study supplementation: Infants randomized to the treatment group will receive 50 µmol/kg/day of Lcarnitine intravenously for 2 weeks, and infants randomized to placebo will received 5% glucose, similar volume to the L-carnitine group. At two weeks, sufficient carnitine is provided in enteral feeds of either breast milk or infant formula. If no intravenous access is available before the supplementation endpoint, the equivalent dose of enteral study supplement (L-carnitine or placebo) will be administered.⁴¹ Parenteral and enteral nutrition will be provided according to standard NICU protocol.

Of note, as many as 10% of the infants in the study will likely continue to rely primarily on parenteral nutrition beyond the proposed two-week supplementation period. Enteral feeds may be withheld from these infants due to underlying illnesses such as sepsis or gastrointestinal disorders like necrotizing enterocolitis. Due to the presence of underlying illness, these infants are at an even higher risk for developing developmental delays.⁴²Therefore, in study patients who are not receiving adequate enteral nutrition (100 cc/kg/day of enteral intake) after 2-weeks of study supplements, carnitine supplementation will be continued until these infant are receiving adequate enteral feeds; at this point, their physiologic carnitine requirements will be met by enteral nutrition alone.

Timeline of Assessments:

- a. Within 72 hours of birth
 - i. Patient enrollment and initiation of study protocol

- ii. Initial carnitine panel drawn
- iii. Initial aEEG reading obtained within 2-3 days of study initiation
- iv. Study Supplement begins within 72-96 hours of birth
- b. Two weeks after study initiation
 - i. Study Supplement concludes (in a small sub-set of patients, study supplementation will be continued until enteral feeds reach 100 cc/kg/day)
 - ii. Follow-up carnitine panel drawn (in addition, as blood transfusions may impact carnitine levels, serum carnitine profiles will be drawn prior to blood transfusion administered between the first and second weeks of life)
- c. aEEG readings will be obtained within 2-3 days of study initiation and at the following post-menstrual ages: 28 weeks (if infant <27 weeks at birth), 32 weeks', 36 weeks', and at 40 weeks' (if infant is still admitted to the NICU).
- d. 36-38 weeks' corrected age
 - i. Cranial MRI
- e. 40 weeks GA (+/- 2weeks)
 - i. Neurodevelopmental assessment

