- f. Neurodevelopmental assessment at 18-24 months corrected age
 - i. Bayley Scales of Infant and Toddler Development III (BSID-III)
 - ii. Modified Checklist for Autism in Toddlers (M-CHAT)
 - iii. Child Behavior Checklist (CBCL)

Individual Infant Timeline:

 2. Study supplement given (within 24 hours of enrollment for total 2 weeks or until enteral intake is at 100 cc/kg/day) 3. Data collection throughout the NICU course (Growth parameters, fluid and nutrition intake and important hospital events), also includes interview with mother to record demographic information and maternal characteristics 4. Blood carnitine panels – drawn at study enrollment and at the end of the intervention (and again if a blood transfusion is administered within this period) 5. Amplitude-integrated EEG readings – within 2-3 of study enrollment and at 28, 32, 36 and 40 weeks' post-menstrual age (dashed lines) 6. Hearing screens – OAE and BAER during the NICU course 7. Brain MRI at 36-40 weeks' GA 8. NNNS at term-equivalent follow-up visit 	1	Study Enrollment (within 72 hours of birth)	Birth	
 24 hours of enrollment for total 2 weeks or until enteral intake is at 100 cc/kg/day) 3. Data collection throughout the NICU course (Growth parameters, fluid and nutrition intake and important hospital events), also includes interview with mother to record demographic information and maternal characteristics 4. Blood carnitine panels – drawn at study enrollment and at the end of the intervention (and again if a blood transfusion is administered within this period) 5. Amplitude-integrated EEG readings – within 2-3 of study enrollment and at 28, 32, 36 and 40 weeks' post-menstrual age (dashed lines) 6. Hearing screens – OAE and BAER during the NICU course 7. Brain MRI at 36-40 weeks' GA 8. NNNS at term-equivalent follow-up visit 				0 hours
 3. Data collection throughout the NICU course (Growth parameters, fluid and nutrition intake and important hospital events), also includes interview with mother to record demographic information and maternal characteristics 4. Blood carnitine panels – drawn at study enrollment and at the end of the intervention (and again if a blood transfusion is administered within this period) 5. Amplitude-integrated EEG readings – within 2-3 of study enrollment and at 28, 32, 36 and 40 weeks' post-menstrual age (dashed lines) 6. Hearing screens – OAE and BAER	2.	24 hours of enrollment for total 2 weeks		72 hours

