 - a. Study patients will be followed at 40 weeks PMA (+/- 2 weeks) to assess neurodevelopmental outcomes among survivors (including incidence of cerebral palsy, neurobehavioral delay, blindness and deafness). Patient information such as weight, length, head circumference, and inter-current illness will be recorded. Infants will be tested using the NICU Network Neurobehavioral Scale, and their scores recorded.
 - Study patients will be followed at 18-24 months corrected age to assess neurodevelopmental outcomes. During this follow-up visit, we will administer the following:
 - i. Bayley Scales of Infant and Toddler Development, Third Edition (BSID-III)
 - ii. Modified Checklist for Autism in Toddlers (M-CHAT)
 - iii. Child Behavior Checklist (CBCL)

Amplitude-integrated EEG measurements (aEEG)

It has previously been reported that background aEEG activity is concordant with the neurological examination and with background patterns on full-scale EEG.^{43,44} Furthermore, in preterm infants, aEEG appears to have a predictive value for developmental outcomes at 3 years of age.⁴⁵ We will, therefore, use aEEG recordings for neurophysiological assessments in our study population. Sedation is not required for this procedure.

We will perform 3-hour aEEG recordings within 2-3 days of initiation of carnitine or placebo supplementation and then at the following PMA: 28 weeks', 32 weeks', 36 weeks', and at 40 weeks' PMA if infant is still admitted to the NICU. aEEG readings will be recorded from the surface of the brain using surface disc electrodes and a Cerebral Function Monitor (CFM) System (Olympic Brainz Monitor; Natus Medical Inc., San Carlos, CA). The Brainz monitor is a bedside brain monitor designed for continuous use in the NICU environment. With its 2-channel capability, this system offers clinicians the ability to monitor brain function at the bedside displaying both real time EEG activity and a time-compressed trend of EEG called amplitude integrated EEG (aEEG) from both cerebral hemispheres. The EEG recordings are stored as downloadable digital files for offline analysis and archiving. The quality of the recording will be monitored by continuous impedance tracing. The tracings will be assessed for both quantitative and qualitative characteristics observed in the whole tracing. We will assess the following: (1) continuity, (2) sleep-wake cycling, (3) voltage and span or bandwidth of the signals, and (4) presence or absence of seizure activity.

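### The first aEEG has three different timing anchors and none places it before the first dose, so secondary aim 3 has no clean baseline, although a pre-dose recording is usually feasible.

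*Combined protocol and SAP*

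**What the plan says.** Secondary Aims, item 3, is "Enhanced brain maturation as measured by amplitude-integrated EEG (aEEG) measurements obtained during the hospital course". The first recording is timed in three places:

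- **Amplitude-integrated EEG measurements:** "within 2-3 days of initiation of carnitine or placebo supplementation". The anchor is the first dose.
- **Timeline of Assessments, item (a)(iii):** "Initial aEEG reading obtained within 2-3 days of study initiation". This sits under a heading for the first 72 hours of life, one line above the start of supplement. Item (c) repeats the same anchor.
- **Individual Infant Timeline, item 5:** "within 2-3 of study enrollment and at 28, 32, 36 and 40 weeks' post-menstrual age". The anchor is enrolment, and no unit is printed after 2-3.

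On the surrounding schedule, Methods/Design states "Informed consent will be obtained from the parents of eligible patients as early as possible within 72 hours of birth". The Timeline of Assessments states "Study Supplement begins within 72-96 hours of birth", while the Individual Infant Timeline has the supplement given within "24 hours of enrollment for total 2 weeks". On duration, the aEEG section says "We will perform 3-hour aEEG recordings". The protocol describes the recordings as non-invasive and done by study personnel. Later recordings are set by postmenstrual age: 28 weeks (for infants born before 27 weeks, per the Timeline of Assessments), 32, 36, and 40 weeks if still admitted.

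Under Statistical Analyses, Outcome Measures plans unpaired comparisons between arms. Logistic regression may adjust for gestational age, birth weight, race, gender and Apgar scores. aEEG is not named there, and no section calls the first aEEG a baseline.

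**The concern.** A recording labelled initial, listed beside the initial carnitine panel and above the start of supplement, looks meant to describe the infant's starting state. The panel is fixed at enrolment; the aEEG is not. Staff can follow the protocol and record one infant before the first dose and another two or three days after it. The resulting variable is neither a pre-treatment measure nor an on-treatment measure at a fixed time.

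Entry runs from 23 to 31 6/7 weeks, so early brain activity will probably vary widely. Randomisation is stratified by gestational age and SGA status, not by any neurological measure, and the listed adjustment factors contain none. A pre-dose tracing would supply one. It would also show whether infants lost before later readings differed between arms at the start. That is useful in a trial that expects to lose about 50 of 150 infants and takes the 40-week aEEG only in those still admitted.

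**Working it through.** The documents give no sample size or power for the aEEG aim, so there is no figure to reproduce. The check is arithmetic on the stated windows.

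**1. How late can the first reading be?** Inputs: enrolment at 0-72 h after birth; first dose at 72-96 h after birth, or within 24 h of enrolment; aEEG within 2-3 days (48-72 h) of its anchor. Days are assumed where the unit is missing.

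| Anchor | Latest first reading | Relative to first dose |
|---|---|---|
| Start of supplement, dose at 72-96 h | 72 + 48 = 120 h to 96 + 72 = 168 h after birth | 48-72 h after |
| Enrolment, dose within 24 h of it | enrolment + 48 to 72 h | at least 48 − 24 = 24 h to 72 − 24 = 48 h after |
| Enrolment at 48 h, dose at 72-96 h | 96 to 120 h after birth | 96 − 96 = 0 h to 120 − 72 = 48 h after |
| Enrolment at 72 h, dose at 72-96 h | 120 to 144 h after birth | 120 − 96 = 24 h to 144 − 72 = 72 h after |

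Study initiation is ambiguous. Item (a)(i) of the Timeline of Assessments pairs it with enrolment. Item (b) ends the two-week supplement two weeks after it, which implies the first dose. Either way it falls under a row above.

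With dosing at 72-96 h, the enrolment anchor closes before the first dose only for infants enrolled by 72 − 72 = 0 h to 96 − 48 = 48 h, depending on which ends of the windows apply. No anchor guarantees a pre-dose reading for all infants.

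**2. Treatment already given.** Up to 2/14 = 14% to 3/14 = 21% of a 14-day course under the aEEG section's wording. The actual mix of pre-dose and post-dose readings cannot be computed, because the documents do not give the distribution of enrolment or recording times.

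**3. Do later readings fill the gap?** No. An infant born at 31 5/7 weeks reaches 32 weeks 2 days (48 h) after birth, before a 72-96 h start. An infant born at 24 weeks reaches 28 weeks on day 28, after a 14-day course begun on day 3-4 has ended (day 17-18). Only the first reading can be a common pre-dose measure.

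**4. Is there time for a 3-hour recording?** With dosing at 72-96 h, the gap after enrolment at hour e is 72 − e to 96 − e:

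- e = 48: 24-48 h
- e = 69: 3-27 h
- e = 72: 0-24 h

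Under the 24-hour rule the gap is anything from 0 to 24 h. There is usually time, but not always.

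**5. What a baseline could be worth.** For a continuous outcome with linear adjustment, the proportional fall in residual variance is r², where r is the correlation of the pre-dose reading with the later one beyond stratum. The documents give no r. Assuming 0.3 to 0.6: 0.3² = 0.09 and 0.6² = 0.36, a cut of 9-36%. If the planned covariates explain part of the same variation, the additional gain is smaller.

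**The case against.** The strongest reply is that the trial does not need this baseline. It is randomised, placebo-controlled and blinded to clinicians and nurses, and the plan compares arms without pairing. A comparison at the same postmenstrual age is valid with no starting value. That stands, and it limits the point.

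Four stronger readings are tempting, and the documents do not support them:

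- **That chance imbalance in early brain function could not be separated from a treatment effect.** Chance imbalance is what randomisation and the confidence interval account for. The loss is precision and a balance check, not validity.
- **That variation between immature and more mature infants could not be removed.** Gestational age is a stratification factor and a listed adjustment factor. Fixed-age readings also align infants by maturity, CRIB scores and head ultrasounds are collected, and Grade IV haemorrhage or seizures in the first 72 hours are excluded.
- **That an early carnitine effect will be subtracted out.** This would follow only if an on-treatment reading were used as baseline. No change-from-baseline aEEG analysis is planned, and aim 3 can be read as level at a given age.
- **That the omission costs a known number of infants.** The range 1/(1 − 0.09) − 1 = 10% to 1/(1 − 0.36) − 1 = 56% rests wholly on the assumed correlation. It does not apply to presence or absence of seizures or to other qualitative aEEG features.

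Two further replies have some force. The Timeline of Assessments may intend a pre-dose reading and simply be loosely worded, but this is a reason to state it. And an infant enrolled near 72 hours, or dosed almost at once after enrolment, may have no time for a tracing, so any covariate plan needs a rule for missing baselines.

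**Conclusion.** The point holds as an inconsistency and a missed, cheap improvement for one secondary aim. The three anchors conflict, and none requires the first aEEG before the first dose. Under the aEEG section's wording it may come up to 2-3 days into treatment. As written, the first reading cannot serve as a clean baseline.

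This does not make the planned arm comparisons biased. The consequences are lower precision, no check of balance in starting brain function, and no sound analysis of within-infant change. The 9-36% variance figure is an illustration: it assumes a residual correlation of 0.3-0.6, a continuous measure and linear adjustment, and it is an upper guide if the planned covariates overlap with the baseline. The change should be made, but the trial's validity does not depend on it.

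**What to change.** - **Timing.** Reconcile the Timeline of Assessments (items a and c), the Individual Infant Timeline (item 5, including its missing unit) and the aEEG section, so that the first 3-hour aEEG is recorded after enrolment and before the first dose. Do not change when supplement starts.
- **Start-of-supplement wording.** The 72-96 h rule and the 24-hours-from-enrolment rule cannot both be met for an infant enrolled before 48 h, since e + 24 is then below 72. The investigators must reconcile these passages; this point takes no position on which applies.
- **Record keeping.** Log the time of the recording relative to the first dose for every infant.
- **Analysis.** Pre-specify the pre-dose reading as a covariate, alongside gestational age, in a linear model for later continuous aEEG measures. The plan currently names only logistic regression for adjustment.
- **Missing baselines.** State a method that keeps every infant in the analysis, for example a missing indicator. Do not use a post-dose first reading as baseline; report it descriptively with its timing.

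The cost is small. The number of recordings is unchanged and the first one moves earlier by at most a few days. Study staff at both hospitals must be able to record soon after consent, and some late-enrolled infants will have no pre-dose tracing.

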- 1. Patient demographics: date of birth, birth weight, gestational age as determined by best obstetric estimate or Ballard score, SGA or LGA status, Apgar scores, birth history, delivery room management, gender, ethnicity.
- 2. Maternal characteristics: maternal age, maternal language, ethnicity, presence of prenatal care, type of insurance coverage, maternal educational status, presence of maternal depression, teratogen exposure (alcohol, tobacco or illicit drug use during pregnancy), antenatal steroid use, hypertension/pre-ecclampsia, gestational diabetes/Type I or II diabetes, and maternal infections.
- 3. Management of fluid and nutrition: daily fluid intake and urine output, glucose infusion rate, total caloric intake, total protein intake, and food efficiency (weight gain divided by caloric intake) while on study supplement.
- 4. Hospital course:
 - a. Growth parameters: weight, length and head circumference at birth, daily weight until birthweight regained and then weekly, weekly length, and head circumference two times per week for four weeks)
 - b. Cardiovascular: need for vasopressors, presence of PDA (including medical or surgical treatment; platelet count and mean fluid intake at time of treatment)
 - c. Gastrointestinal: feeding intolerance, NEC, presence of gastrointestinal reflux,
 - Neurological: results of aEEG readings, results of head ultrasounds including presence of germinal matrix/intraventricular hemorrhage and periventricular leukomalacia, cranial MRI results
 - e. Opthalmological: grade of retinopathy of prematurity and treatment or ophthalmologic diagnosis,
 - f. Hematologic: transfusion history including dates
 - g. Infectious disease: presence of concurrent presumed and proven infection,
 - h. Other: performance of any surgical procedures, duration of intravenous access, use of medications, and hearing screen results (OAE and/or ABR) with observed thresholds of hearing frequencies.
 - i. Clinical Risk Index for Babies (CRIB) scores will be calculated for each infant.
 - j. We will also monitor for possible short-term side effects.
- 5. Discharge information: weight, length, head circumference, and diagnoses at time of discharge, routinely-ordered discharge brain MRI findings
- 6. Neurodevelopmental assessment:

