These aEEG recordings are non-invasive and do not create additional risk for the patient. These aEEG readings will be performed by study personnel and will be provided at no additional cost to the patient.

MRI Brain Imaging

Imaging of the brain at term-equivalent is the standard of care for the evaluation of preterm infants prior to being discharged home. In our Neonatal Intensive Care Units, we routinely obtain brain MRI at \geq 36 weeks' corrected age (prior to discharge home). The MRI examination is performed in sleeping infants after they have been fed; therefore, sedation is not required for the procedure. MRI will be performed per routine protocol at 36 weeks' corrected age, prior to discharge home. Brain growth will be assessed on anatomical images, through manual segmentation of the basal ganglia, cerebellum and whole brain. White matter development will be assessed on diffusion tensor imaging (DTI), using the tract-based spatial statistics method. The DTI measures fractional anisotropy and mean diffusivity, which have previously been shown to be abnormal in ex-preterm children; these will be compared in multiple white matter regions (cerebral peduncle, posterior limb of the internal capsule, corona radiata, corpus callosum, and optic radiations).^{37,46,47}

Brain metabolism will be assessed using proton MR spectroscopy, obtained from both white matter (centrum semiovale) and gray matter (basal ganglia) structures. The relative concentrations of the brain metabolites choline, creatine and n-acetylaspartate (NAA) will be compared between control and carnitine-supplemented children. Each metabolite reflects specific cellular and biochemical processes. NAA is a neuronal marker and decreases with any disease that adversely affects neuronal integrity. Choline is a constituent of cell membranes and an intermediate of phospholipid metabolism. Choline levels on MR spectroscopy increase with increased membrane turnover, and are taken as a measure of cell proliferation. Creatine plays a role in maintaining energy-dependent systems in brain cells by serving as a reserve for high energy phosphates. Because the creatine peak remains fairly stable even in face of disease, it may be used as a control value.⁴⁸ In children born preterm, the NAA/Choline ratio at term-equivalent age correlates with later cognitive development.⁴³

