These measurements will be obtained through brain MRIs routinely obtained in preterm infants prior to discharge. There will be no change in the routine protocol in order to obtain these outcomes. The reading and analyses of these MRIs will be performed at no additional cost to the study subject.

Neurobehavioral Assessment:

Infants discharged from the Weiler and Montefiore North Division NICUs routinely follow-up with our neonatologists at term-equivalent age. At this visit, the infants routinely receive a neurobehavioral

assessment. We have chosen to administer the NICU Network Neurobehavioral Scale due to its prevalence of use in neonatal research and its strong psychometric properties.⁴⁹

The NICU Network Neurobehavioral Scale (NNNS) was developed by [name]., & [name].⁵⁰ The scale is intended for use with use with healthy and at-risk preterm infants and full term infants at risk because of prenatal substance exposure or other conditions. The NNNS can be utilized in either a clinical or research setting in order to obtain a comprehensive assessment of neurobehavioral functioning. There is a focus on neurologic, stress, and withdrawal signs. The tool may be used with infants through 6 weeks of age and may be used as early as 30 weeks for preterm infants. The exam assesses 115 items in three categories:

- Neurological items: active and passive muscle tone, primitive reflexes, and central nervous system integrity
- Behavioral state, sensory, and interactive responses
- Stress/abstinence items

The examiner assesses the items. Summary scores are generated for stress, withdrawal, and the major domains of neurobehavioral performance. The NNNS is administered in a standardized format which allows objective assessment of the infant. Normed scores are available for at-risk and healthy infants. Because the assessment is relatively new, there are no long-term studies looking at predictive validity. However, the test is based upon a variety of prior tools, where long-term predictive validity has been shown.⁵¹ The test takes approximately 20 minutes to administer. (Ordering information: http://www.brookespublishing.com/store/books/lester-7659/index.htm)

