The effect of L-carnitine supplementation on outcome measures in enrolled infants will be examined for significance by comparing the two groups using unpaired data analysis with the assistance of a statistician. Continuous data (percent weight loss, time to regain birthweight, NNNS score, BSID-III scores) will be compared between the "placebo" and the "carnitine supplemented" groups by unpaired student t-test (a 2 tailed P value <0.05 will be considered to indicate statistical significance) or Wilcoxon's rank sum test for non-parametric parameters. Unmatched nominal data will be compared using Fisher's Exact Test or Chi-square test as required (e.g.: presence or absence of normalization of the carnitine profile; or presence or absence of pathological findings on the discharge MRI). Logistic regression models will be used to adjust for potentially confounding factors including gestational age, birth weight, race, gender, Apgar scores.

Risks and Discomforts:

A brief description of the risks and discomforts associated with this study is included in the protocol consent form and will be discussed in detail with each family at the time of study enrollment.

Carnitine is routinely administered with parenteral nutrition in approximately one-third of the neonatal intensive care units in the United States, although not in the Jack D. Weiler Hospital or Montefiore North Division NICU's. Carnitine is FDA-approved, and there have been no reports of severe toxicity from

overdose. Data available from the adult literature reports side effects of mild gastrointestinal symptoms such as gastritis, vomiting, diarrhea or abdominal cramping; body odor; and seizures, in patients with or without a known seizure disorder. These side effects are dose-dependent and might be avoided by slow consumption of the solution or greater dilution. One investigator reported transient elevation of triglycerides and increased platelet aggregation in uremic patients with severe renal insufficiency who received high doses of carnitine supplementation.⁵²

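### The MRI brain-growth outcome is attained volume at a single scan, and the planned unadjusted comparison is less precise than the baseline data already collected would allow

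*Combined protocol and SAP*

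**What the plan says.** Secondary aim 4 reads "Fewer abnormal findings, better brain growth, white matter development and brain metabolism on brain magnetic resonance imaging (MRI"), with the scan at 36-40 weeks. The MRI Brain Imaging section gives the measurement: "Brain growth will be assessed on anatomical images, through manual segmentation of the basal ganglia, cerebellum and whole brain". No scan is planned before treatment: "These measurements will be obtained through brain MRIs routinely obtained in preterm infants prior to discharge".

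Head size before treatment is recorded. Data collection, item 4a, lists "weight, length and head circumference at birth", then head circumference twice a week for four weeks. Supplementation starts 72-96 hours after birth (Timeline of Assessments), so the birth value precedes the first dose. The stated use of these data is secondary aim 1: "Increased rate of growth of head circumference within the first month of life and increased food efficiency".

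Outcome Measures says that the effect on outcomes "will be examined for significance by comparing the two groups using unpaired data analysis". Continuous data get a t-test or rank sum test; MRI volumes are not among the examples named. Adjustment is by logistic regression on factors that include gestational age, birth weight, race, gender and Apgar scores. Randomization is stratified into three gestational-age bands and a small-for-gestational-age (SGA) group, in blocks of 4.

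The time of the scan varies between sections. MRI Brain Imaging says "MRI will be performed per routine protocol at 36 weeks" (and, for routine practice, 36 weeks or later). Timeline of Assessments gives 36-38 weeks. Secondary aim 4 and the Individual Infant Timeline give 36-40 weeks.

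**The concern.** There are two linked problems.

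The first is the name. Growth is change over time, and one scan gives size at one time. The protocol keeps this distinction for head circumference, where aim 1 is a rate from serial measurements, but not for MRI.

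The second is precision. Infants differ in head size before any study supplement is given. In an unadjusted test, whatever part of that variation persists to the scan stays in the error term. A relevant pre-treatment measurement is collected, but no analysis of the volumes uses it. The one adjustment method in the plan is for binary outcomes. If adjustment is wanted later, the model and covariates would have to be chosen after the data are seen.

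At stake is the sensitivity of a secondary outcome, and how far a chance imbalance in head size at birth could blur its reading.

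**Working it through.** **Inputs from the documents.** 50 infants per arm, a difference of 0.5 SD, alpha 0.05 and power 0.80 (Sample size); two-tailed testing (Outcome Measures). The plan sizes the primary outcomes only and states no power for MRI volumes; 50 per arm and 0.5 SD are borrowed here as a yardstick.

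**Input not in the documents.** r, the correlation of the baseline covariates with MRI volume (the multiple correlation if there are several). It is assumed, and shown as a range.

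**1. The plan's own figure.** The noncentrality is d × sqrt(n/2) = 0.5 × sqrt(25) = 2.5, with 98 degrees of freedom. Power is 0.80 one-sided (0.799) but 0.697 two-sided. The stated 0.80 therefore reproduces only one-sided. The starting value of 0.70 below reflects that separate matter and is not caused by the lack of adjustment.

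**2. Is the unadjusted difference biased?** No. In 20,000 simulated trials of 50 per arm with a true difference of 0.5 SD, the unadjusted estimate averaged 0.498-0.499 at r = 0.3, 0.5 and 0.7. Adjustment changed only the standard error:

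| r | SE unadjusted | SE adjusted |
|---|---|---|
| 0.3 | 0.201 | 0.193 |
| 0.5 | 0.199 | 0.174 |
| 0.7 | 0.199 | 0.142 |

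**3. Precision gained.** Residual variance is 1 − r², so the effective difference is 0.5/sqrt(1 − r²). Two-sided power with 50 per arm:

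| r | Variance removed | Effective d | Power |
|---|---|---|---|
| 0 (as planned) | 0% | 0.500 | 0.697 |
| 0.3 | 9% | 0.524 | 0.737 |
| 0.45 | 20% | 0.560 | 0.792 |
| 0.6 | 36% | 0.625 | 0.872 |

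The proposed model uses five more degrees of freedom than the t-test (three for stratum, one each for head circumference and age at scan), leaving 93 instead of 98. That lowers each power figure by less than 0.001.

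**4. Chance imbalance in birth head size.** The standard error of a standardised difference is sqrt(2/50) = 0.20, so the 95% range under simple randomisation is ±1.96 × 0.20 = ±0.39 SD. The design is stratified, so this is an upper figure. If strata explained half the variance in birth head size (assumed), the range would be ±0.39 × sqrt(0.5) = ±0.28 SD. An imbalance at the edge of the range moves the volume difference by r times its size, taking r here as the correlation of birth head size with volume:

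| r | From ±0.39 SD | From ±0.28 SD |
|---|---|---|
| 0.3 | 0.12 SD | 0.08 SD |
| 0.45 | 0.18 SD | 0.12 SD |
| 0.6 | 0.24 SD | 0.17 SD |

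**The case against.** The strongest reply is that nothing here is invalid. Arms are randomised before treatment, so the expected difference in attained volume equals the expected difference in growth since randomisation. A single scan can therefore address aim 4 between arms, and chance imbalance is already covered by the 0.05 error rate. This stands. A reader might infer that head size fixed before treatment dilutes the effect, pulling it towards zero. The design does not support that, and step 2 shows no such shift: the cost is variance only.

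A reader might also infer that the plan ignores baseline differences or head circumference altogether. It does not. Gestational age and SGA are stratified, gestational age and birth weight are named for adjustment, and head circumference serves aim 1. What remains is that an unadjusted test takes no precision from the stratification, and that logistic regression cannot adjust a continuous volume.

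The size is open to challenge too. The correlation is undocumented, and at 0.3 the gain is only 4 percentage points of power. The table credits the whole gain to the covariates against a model with none. What birth head circumference adds beyond stratum has not been computed and is probably smaller. Finally, head circumference is not brain volume, and still less basal ganglia or cerebellar volume. It can serve as a covariate but, being in different units, cannot be the baseline of a change score. These limits stand, and they are why the recommendation concerns precision and naming only.

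**Conclusion.** The point holds as one of precision and labelling. Aim 4's brain-growth outcome is attained volume at one pre-discharge scan. The planned comparison is unbiased but less precise than the collected data allow, and the plan contains no adjusted analysis suited to a continuous volume.

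For a 0.5 SD difference, two-sided power at 50 per arm would rise from 0.70 to about 0.74, 0.79 or 0.87 at assumed correlations of 0.3, 0.45 or 0.6. This supposes that all 50 per arm have a usable scan. Chance imbalance in birth head size has a 95% range no wider than about ±0.39 SD, and about ±0.28 SD if strata explain half its variance.

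The documents do not support a claim that the MRI comparison is invalid or biased, or that the trial's main result is at risk. The outcome is secondary, no power was promised for it, and the primary outcomes are unaffected. The change is still worth making, because it needs no new data.

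**What to change.** - **Outcome Measures:** state that each segmented volume (basal ganglia, cerebellum, whole brain) is compared by a linear model (ANCOVA) with study arm, randomisation stratum, head circumference at birth and postmenstrual age at scan. Age at scan is observed after randomisation and the scan is tied to discharge, so also report the model without it.
- **Secondary aim 4 and MRI Brain Imaging:** name the outcome as brain volume at the pre-discharge MRI, adjusted for head size at birth, instead of brain growth.
- **Scan window:** reconcile the 36, 36-38 and 36-40 week statements across Secondary Aims, Timeline of Assessments, Individual Infant Timeline and MRI Brain Imaging.

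The cost is a few sentences and five degrees of freedom (98 to 93). No extra scan, visit or blood sample is needed. The date of the scan must be kept with the MRI result so that age at scan can be calculated.
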